4.2 NUMBER OF PARTICIPANTS

15 participants with ILD will be recruited in the Lothian region, and another 15 participants in the Royal Victoria Infirmary, Newcastle upon Tyne Hospital (for

10

participants from Newcastle). The length of recruitment period will be approximately 6 months.

4.3 INCLUSION CRITERIA

- 1.- Fibrosing lung disease on HRCT obtained from medical records, defined as reticular abnormality with traction bronchiectasis with or without honeycombing, with disease extent of >10%, performed within 24 months of screening visit Clinical stability concerning pulmonary infections or acute exacerbations within the previous four weeks of inclusion in the study.
- 2.- Absence of recent Myocardial Infarction (within last 3 months), unstable angina, other significant cardiac problems, systolic blood pressure > 180 mmHg, diastolic blood pressure > 100 mmHg or tachycardia (higher than 100 bpm)
3. - Absence of significant orthopaedic, neurological, cognitive and/or psychiatric impairment restricting mobility.
4. - Not following any exercise programme in the last 3 months.
5. - Participants between 18 and 85 years old will be recruited and with ability to give informed consent.
6. - TLCO \geq 25% and \leq 80% predicted. FVC (or VC) \geq 45%
7. -Patients that experience a drop in oxygen saturation with exercise below 90%

4.4 EXCLUSION CRITERIA

1. - Emphysema greater than extent of fibrosis on high resolution computed tomography (HRCT) of the thorax.
2. - FEV1/FVC ratio < 70%.
3. - Participants should not be taking part in other interventional studies currently. Our research is not a CTIMPs and co-enrolment will not be allowed under any circumstances.
4. - Absolute contraindications for cardiopulmonary exercise testing, which are:
 - a. - Unstable angina
 - b. - Uncontrolled arrhythmias causing symptoms or hemodynamic compromise.
 - c. - Syncope.
 - d. - Active endocarditis.
 - e. - Acute myocarditis or pericarditis.
 - f. - Symptomatic severe aortic stenosis.
 - g. - Uncontrolled heart failure.
 - h. - Acute pulmonary embolus or pulmonary infarction.
 - i. - Thrombosis of lower extremities.
 - j. - Suspected dissecting aneurysm.
 - k. - Uncontrolled asthma.

- l. - Pulmonary edema.
- m. - Room air desaturation at rest $\leq 85\%$
- n. - Respiratory failure.
- o. - Acute no cardiopulmonary disorder that may affect exercise performance or be aggravated by exercise (i.e. infection, renal failure, thyrotoxicosis)
- p. - Mental impairment leading to inability to cooperate.

4.5 RECRUITMENT, CONSENT AND SCREENING

All Patients affected with interstitial lung diseases referred to the physiotherapy department to receive pulmonary rehabilitation in the Lothian region and Newcastle, also those from the ILD clinic will be invited by a member of the direct care team ([name] in Edinburgh and [name] in Newcastle) to participate and will receive a patient's information sheet with an invitation to attend pre-assessment for this study. This appointment should occur at least 3 days after the patient has received the Patient Information Sheet. This is to ensure that the patient has adequate time to consider his or her decision to participate in the study. At pre-assessment, the study will be explained to them and written informed consent will be obtained from those agreeing to participate.

4.6 WITHDRAWAL OF STUDY PARTICIPANTS

Participants are free to withdraw from the study at any point or a participant can be withdrawn by the Investigator. If withdrawal occurs, the primary reason for withdrawal will be documented in the participant's case report form, if possible. The participant will have the option of withdrawal from:

- (i) All aspects of the trial but continued use of data collected up to that point. To safeguard rights, the minimum personally-identifiable information possible will be collected.
- (ii) The study will be stopped on patients that are presenting an acute exacerbation of their lung condition or unable to perform the exercise test. These patients will receive adequate treatment and the study will be delayed. Patients with disease progression that prevents them to continue their participation will be discontinued from their participation in the study.

4.7 BASELINE MEASUREMENTS

All the visits will take place in ward 204 (Respiratory Medicine) of the Royal Infirmary of Edinburgh (for participants from Scotland) and in the Royal Victoria Infirmary, Newcastle upon Tyne Hospital (for participants from Newcastle).

The visits during the first day before and after the intervention will take 2 hours each, and the following tests will be performed:

- Consent firstly will be re-confirmed at this visit.

- A blood test will be taken (6 ml) to know the levels of blood biomarkers associated with fibrosis that have been shown to be associated with disease progression (Inc. but not restricted to PAI-1, VEGF-A, PDGF-AA, PDGF-BB, Cystatin-C, Angiopotein-1, HE4/WFDC-2).
- A quadriceps maximal voluntary contraction test (QMVCT) will be taken to measure the strength of the quadriceps muscle.
- The shortness of breath will be assessed using the Modified version of the Medical Research Council scale (mMRC).
- Height.
- Weight.
- A Cardiopulmonary Exercise Test (CPET).
- A Constant work rate Cycle Test (CWRCT) at 75% of peak work rate (obtained from a maximal exercise test conducted beforehand) will be carried out.
- During this visit the PI will deliver to the participants the Actigraph GT3x activity monitor, which will have to be used at home for 1 week before and 1 week after of the intervention to measure the physical activity levels in daily life. The participants will have to return it during their post intervention appointment.
- Also during this visit two questionnaires called St George's Respiratory Questionnaire (SGRQ), which measure the quality of life will be delivered by the PI to be answered at home, the first one must be answered 1 day before of the intervention and returned during the first day of the intervention and the second one will have to be answered 1 day after of the intervention and returned during the post intervention appointment.
- Finally another 2 questionnaires called Hospital Anxiety and Depression Scale (HADS), which measure the anxiety and depression levels likewise will be delivered by the PI to be answered at home, the first one must be answered 1 day before of the intervention and returned during the first day of the intervention and the second one will have to be answered 1 day after of the intervention and returned during the post intervention appointment.

The participants will be able to rest for about 20 minutes between each test and we will offer them refreshments. Oxygen will be supplied, when needed, via nasal cannula and titrated to maintain a $SpO_2 \geq 88\%$.

4.8 RANDOMISATION

Following confirmation of eligibility by the CI or PI and signature of the informed consent, patients will be randomised using sealed letters to HIIT plus HFNO or HIIT plus nasal cannula. Patients will be sequentially randomised. Randomisation code and sealing of envelopes will be done by the research nurses and stored in a room at RIE and Royal

Victoria Infirmary accessible with a key. This will be done before any baseline procedures.

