4.9 BLINDING

In this open label study patients will not be blinded with respect to the modality of oxygen delivery but will not know the dose of oxygen they will be receiving or their SpO2 during the pulmonary rehabilitation program and the tests.

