4.10 INTERVENTION

The intervention consists of HIIT plus HFNO versus HIIT plus oxygen delivered through a nasal cannula. The oxygen delivered via HFNO will be between 31 and 37°C according to patient preference. To minimize condensation, the heated humidified gas is delivered via heated tubings through a wide-bore nasal prong. Air flow will be 50 L/min and FiO2 will be titrated to maintain SpO2 above 88%. The comparator will be oxygen delivered via nasal cannula titrated to the same SpO2. Both HIIT will be performed at the same workload, which will be progressive throughout the 8 weeks and will be modified during each session in order to achieve a Borg score of 5, starting with high load intervals at 60% of the maximal watts achieved beforehand during a maximal CPET divided by lower load intervals at 40% maximum load during the first week, and finishing with high load intervals at 110% maximum load separated by load intervals at 80% maximum load in the last weeks (see Appendix A and C).

Basically the participants will have to pedal in a stationary bicycle for 30 minutes, during the other 20 minutes the patients will do exercises for their upper limbs using Thera bands and dumbbells. Muscles of upper limbs to work will be deltoids, pectorals and biceps (3 series of 10 repetitions each). Finally the participants will receive 10 minutes of respiratory physiotherapy including techniques to eliminate phlegm, breathing exercises and ludic activities to train the respiratory muscles such as inflating balloons.

Which group will use HFNO or conventional oxygen will be randomly selected from a sealed envelope. Randomized means that all participants will have the same chance of belonging to one group or another, they must choose a sealed envelope and inside it will be written to which group they will belong.

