4.11 DURATION OF THE STUDY

In general, the study will consist of 8 weeks of intervention plus 1 day of evaluations before and after the intervention. The window between the baseline appointment and the first day of the intervention can be from 1 to 30 days, and the window between the last day of intervention and the post intervention appointment will be from 8 to 38 days.

Assessment	Screening	Baseline Appointment	To be done at home	Intervention (8 weeks)	Post-Intervention Appointment
-------------------	-----------	----------------------	--------------------	----------------------------	-------------------------------

		(1 st day before Intervention)	(Pre &Post Intervention)		(1 st day after Intervention)
Assessment of eligibility criteria	X				
Written informed consent	X				
Demographic data, contact details	X				
Randomisation	X				
Weight		X			X
Height		X			
Blood Test		X			X
Blood Pressure		X			X
QMVCT		X			X
mMRC		X			X
CPET		X			X
CWRCT		X			X
Physical activity levels in daily life			X		
SGRQ (Questionnaire)			X		
HADS (Questionnaire)			X		
Intervention 1 st Group HIIT + HFNO				X	
Intervention 2 nd Group HIIT + NC				X	

Observation: There will be continual ECG monitoring during all the tests.

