Appendix C

Administration of Oxygen through HFNO and Nasal Cannula.

High Flow Nasal Oxygen is a System which delivers heated, humidified high flow oxygen therapy via nasal cannula or tracheostomy attachment. HFNO has become increasingly used for management of patients with type 1 respiratory failure. It delivers high inspiratory gas flow (up to 60 litres per minute), which is warmed and humidified. Oxygen can be titrated from 21-95%. If oxygen exceeds 95%, the oxygen reading will pulse red and the device will alarm.

Benefits include:

- Reversal of hypoxaemia
- Reduced work of breathing
- Improved secretion clearance
- Improved patient tolerance/ comfort

Absolute Contra-indications

- Patients with type 2 respiratory failure requiring Non-invasive ventilation (NIV)
- COVID or suspected COVID infections
- Nasal passage abnormalities or recent nasal surgery
- Cerebro-spinal fluid leaks
- Basal skull fractures
- Severe epistaxis

Equipment

- Fisher & Paykel AIRVO2 TM humidifier

- Opti-flow nasal cannula (small, medium or large) or Tracheostomy Direct Connection. A mask could be used if other options are not appropriate

- Heated breathing circuit and water chamber
- 1l bag of sterile water
- Bubble oxygen tubing

Setting patient up on the HFNO

- Explain procedure to patient/ carer and gain consent.
- Wash hands and wear appropriate Personal Protection Equipment (PPE) in line with infection control policy.
- Assemble equipment as per manufacturer's instructions. Label equipment with date for tubing change (according to manufacturer's instructions). All disposable components are single patient use. Select appropriate patient inter-face. Switch equipment on, connect oxygen supply if required and check it is ready for use (check disinfection status).
- Perform sounding alarm test by disconnecting tube from top of machine to check that alarm sounds.

Adjusting settings

- Press any button to enter the summary screen. Select temperature using the arrow right button. Press and hold down both the up and down arrows at the same time to unlock the screen. Use up and down arrows to select desired temperature. Ideally should be set at 37°C as this will provide optimum humidification but this may not be comfortable so either 34 or 31°C may be selected, if a mask is used then temperature should be set at 31°C.

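### Randomisation at Screening in an open-label trial means every baseline measurement, including the volitional exercise tests, is taken with the arm known

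*Protocol*

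**What the plan says.** Section 4.8 gives the sequence: "Following confirmation of eligibility by the CI or PI and signature of the informed consent, patients will be randomised using sealed letters". It then describes how the envelopes are prepared and stored, and ends with "This will be done before any baseline procedures". The schedule table in section 4.11 has a row for "Randomisation" with its only mark under Screening. Blood pressure, QMVCT, mMRC, CPET and the constant work rate cycle test are first marked at the later baseline appointment. The activity monitor, SGRQ and HADS are completed at home; section 4.7 has the monitor and questionnaires handed out at the baseline visit.

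On knowledge of the arm, section 4.9 says "In this open label study patients will not be blinded with respect to the modality of oxygen delivery". Section 4.10 says of the patients that "they must choose a sealed envelope and inside it will be written to which group they will belong".

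On eligibility, inclusion criterion 7 in section 4.3 reads "Patients that experience a drop in oxygen saturation with exercise below 90" (per cent). The first exercise test in the schedule is the one that section 4.7 lists as "A Cardiopulmonary Exercise Test (CPET"). Appendix C has its own list of absolute contraindications to HFNO, among them "Nasal passage abnormalities or recent nasal surgery".

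**The concern.** The primary outcome, endurance time (section 3.1), ends when the patient gives up, and Appendix B has staff encouraging maximal effort. Baseline CPET watts fix the load of that test at 75% and the nominal training loads at 60% to 110% of maximum (section 4.10). If patients or testers know the arm at baseline, effort or encouragement can differ between groups before any treatment is given. The baseline is then no longer a pre-allocation measurement, and an analysis that uses it can carry the difference into the estimated treatment effect. The self-reported scales and the activity week are open to the same influence.

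The order also moves avoidable losses to the wrong side of randomisation. Section 4.6 stops participation for patients who cannot do the exercise test, and Appendix A checks CPET contraindications while preparing the patient for the test. Some patients will therefore drop out with an allocation who could have been screened out without one.

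**Working it through.** The Protocol states no effect size, SD or dropout rate, and section 6 says that no sample size was calculated, so there is no figure to reproduce. The order of events comes from the text. The numbers below are illustrations on stated assumptions.

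**1. Order of events.** Read alone, the last sentence of section 4.8 could refer only to preparing the envelopes. The schedule settles it: randomisation is at Screening, and the tests are at the baseline appointment. With the envelope shown to the patient and no masking, the arm is known before the first baseline measurement. No section masks the testers.

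**2. Eligibility at the point of allocation.**
- Criterion 7 (exercise desaturation): no exercise test is scheduled before randomisation. The medical-record sources in section 4.12.6 are HRCT, echocardiograms and breathing tests, with no exercise or walk test named.
- Criterion 2 (blood pressure limits): blood pressure is first scheduled at baseline.
- HFNO contraindications: nasal abnormality or recent nasal surgery, cerebrospinal fluid leak, basal skull fracture and severe epistaxis are in Appendix C but not in section 4.4. Type 2 respiratory failure and COVID are arguably covered by the section 4.4 items on respiratory failure and infection.

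**3. How a baseline shift carries through.** Let one arm's baseline be lower by *b* (in SD units), with no true effect, equal SDs and baseline–follow-up correlation *r*.
- Change score: bias = *b*.
- ANCOVA: bias ≈ *r* × *b*. For example, 0.5 × 0.25 = 0.125 and 0.9 × 0.5 = 0.45.
- Final values only: no direct bias.

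Simulated with 20,000 runs, 15 per arm (assumed) and two-sided 0.05 (sidedness assumed):

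| *r* | *b* | Type I error, change | Type I error, ANCOVA | Type I error, final value |
|---|---|---|---|---|
| 0.5 | 0.25 | 0.101 | 0.066 | 0.051 |
| 0.5 | 0.50 | 0.273 | 0.115 | 0.051 |
| 0.7 | 0.25 | 0.140 | 0.097 | 0.050 |
| 0.7 | 0.50 | 0.400 | 0.231 | 0.047 |
| 0.9 | 0.25 | 0.313 | 0.265 | 0.048 |
| 0.9 | 0.50 | 0.838 | 0.733 | 0.050 |

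With *b* = 0, which is what randomising after baseline secures, the change-score and ANCOVA rates lie between 0.047 and 0.051.

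**4. Route through wattage (not modelled).** Appendix B says a returning patient should be tested at the same wattage as before. If that governs the post-intervention test, a baseline CPET shifted by knowledge of the arm also sets the follow-up load. Final values would then not be wholly protected.

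**5. Cost of losses.** Section 4.2 gives 15 per site, not per arm; 15 per arm is assumed. Each loss is 1/15 = 6.7% of an arm. The effect detectable with 80% power is 1.06 SD at 15 per arm, 1.20 SD at 12 and 1.33 SD at 10.

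**The case against.** Several points on the other side stand.

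- A reader might infer that criterion 7 cannot be checked before randomisation, so ineligible patients are bound to be randomised. The Protocol does not support that. Section 4.8 puts confirmation of eligibility first, patients come from rehabilitation referrals and the ILD clinic (section 4.5), and an earlier exercise saturation may be on record. Section 4.12.6 lists source data in general; it does not claim to be a complete list of eligibility sources. What remains is that no source is named.
- A reader might infer that randomised patients will be excluded from the analysis. No rule says so. Section 4.6 allows data already collected to be used, and the analysis population is a matter commonly left to the SAP.
- A reader might infer that the Appendix C contraindications would come to light only in the HFNO arm. The Protocol does not say when they are checked.
- The analysis in section 6 is a Student's t-test between groups, without saying whether on final values or change. On final values most of the baseline-shift bias disappears.
- Some text mitigates the risk. Patients do not know their oxygen dose or SpO2 during tests (section 4.9). Oxygen at the assessments is by nasal cannula in both arms (section 4.7). Training load is adjusted at each session to a Borg target (section 4.10), which weakens the link from baseline watts to training.

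None of this changes the order itself: allocation is known before the volitional tests, and these safeguards do not hide the arm.

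**Conclusion.** The concern holds as a risk created by the order of procedures. The schedule and section 4.8 place randomisation before the baseline appointment, and the open-label envelope makes the arm known for every baseline measure. Whether a shift will occur, in which direction and how large, cannot be read from the Protocol, so a demonstrated bias should not be claimed. If one occurs, a change-score analysis takes it in full and an ANCOVA takes about *r* × *b*. For the assumed shifts of 0.25 to 0.5 SD and correlations of 0.5 to 0.9, type I error runs from 0.10 to 0.84 and from 0.07 to 0.73 respectively. A final-value comparison stays near 0.05 apart from the wattage route. Losses at the baseline exercise test fall after randomisation, at 6.7% of an arm each if there are 15 per arm. The eligibility gaps are gaps in stated sources and in agreement between section 4.4 and Appendix C, not proof of wrong enrolment. The order is worth correcting even in a proof-of-concept study of about 30 patients: the analysis cannot reliably undo a baseline taken with the arm known, and the correction is cheap.

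**What to change.** 1. In the section 4.11 schedule, move the randomisation mark to after the baseline assessments. The first intervention day suits, because section 4.7 already has the baseline SGRQ and HADS returned then, and the 1 to 30 day window after the baseline appointment leaves room.
2. In section 4.8, delete or correct the closing sentence. State that the envelope is opened only once the baseline tests are recorded and every eligibility criterion, including the blood pressure limits, is confirmed for that patient.
3. Name the source used to confirm criterion 7: either a dated exercise record, or the baseline CPET with the oxygen condition specified. The second needs care, because section 4.7 allows oxygen titrated to an SpO2 of at least 88% during the assessments, and a CPET done on oxygen could miss patients who desaturate without it.
4. Reconcile section 4.4 with Appendix C's own list, so that the list is checked for every patient, in both arms, before allocation.

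The cost is amendment wording and having both oxygen set-ups ready for each patient's first session. No extra visit or test is needed.

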4.9 BLINDING

In this open label study patients will not be blinded with respect to the modality of oxygen delivery but will not know the dose of oxygen they will be receiving or their SpO2 during the pulmonary rehabilitation program and the tests.

4.10 INTERVENTION

The intervention consists of HIIT plus HFNO versus HIIT plus oxygen delivered through a nasal cannula. The oxygen delivered via HFNO will be between 31 and 37°C according to patient preference. To minimize condensation, the heated humidified gas is delivered via heated tubings through a wide-bore nasal prong. Air flow will be 50 L/min and FiO2 will be titrated to maintain SpO2 above 88%. The comparator will be oxygen delivered via nasal cannula titrated to the same SpO2. Both HIIT will be performed at the same workload, which will be progressive throughout the 8 weeks and will be modified during each session in order to achieve a Borg score of 5, starting with high load intervals at 60% of the maximal watts achieved beforehand during a maximal CPET divided by lower load intervals at 40% maximum load during the first week, and finishing with high load intervals at 110% maximum load separated by load intervals at 80% maximum load in the last weeks (see Appendix A and C).

Basically the participants will have to pedal in a stationary bicycle for 30 minutes, during the other 20 minutes the patients will do exercises for their upper limbs using Thera bands and dumbbells. Muscles of upper limbs to work will be deltoids, pectorals and biceps (3 series of 10 repetitions each). Finally the participants will receive 10 minutes of respiratory physiotherapy including techniques to eliminate phlegm, breathing exercises and ludic activities to train the respiratory muscles such as inflating balloons.

Which group will use HFNO or conventional oxygen will be randomly selected from a sealed envelope. Randomized means that all participants will have the same chance of belonging to one group or another, they must choose a sealed envelope and inside it will be written to which group they will belong.

